13.2 Serious Adverse Events

Serious Adverse Event (SAE) refers to any event that result in the following

- Death
- Life-threatening AE
- A disability or incapacity
- Inpatient hospitalization due to the therapy. This may not include patients who choose to withdraw from the study and opt to be admitted or patients who are withdrawn from the study for better diuresis in the hospital.
- Persistent or significant incapacity or substantial disruption of the ability to conduct normal life functions.
- Congenital anomaly or birth defect of an offspring

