test. Eligible participants will be educated on device preparation, placement, removal and care in accordance with the Instructions of Use Manual. The screening phase includes evaluation of the home situation to ascertain that sufficient support is or can be made available for at home treatment as an alternative to inpatient care. In appropriate settings, lay caregiver will also be trained.

Pilot Phase.

Patients will be visited daily by Steward Home Care and Hospice for home health nursing services in accordance with standard procedures. Nursing services will include checking vitals, obtaining blood samples and evaluation for clinical improvement or worsening. The first visit will be performed within 24 hours after enrollment.

The first sc2Wear Infusor will be prepared and placed on the patient as part of the training. The patient will go home with the sc2Wear furosemide Infusor in place on the abdomen to be activated upon arrival at home. Participants will be treated with the sc2Wear furosemide Infusor daily for 3 consecutive days at home. Participants will be evaluated by the cardiology service of SEMC within 24 hours after the 3rd dose of sc2Wear furosemide. If a patient was found to have responded satisfactorily but requires additional parenteral diuretics an additional 4 days may be prescribed for a total of 7 consecutive treatments. If additional units are prescribed patients are to be evaluated the cardiology service of SEMC within 24 hours after the last dose of sc2Wear furosemide Infusor.

If the subject requires further parenteral diuresis after the 7 days of at home treatment, they will be converted to usual care at that time, which may require inpatient care. Participants will be instructed to record daily morning weights during and after treatment until the second post treatment evaluation.

Interim clinic visits and laboratory assessments may be required based on clinical considerations.

The following parameters will be studied at Baseline and follow-up treatment visits.

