STATISTICAL ANALYSIS	
Primary Outcome
 
Description of treatment effect and as described in the study endpoints.
 
Description of the seriousness, severity, relatedness of all adverse events observed during the study period.

1)

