6.3 REMOVAL OF SUBJECTS FROM THE STUDY

All patients who are withdrawn from the study will still need to be monitored closely for 30 days for their safety. The following will be reasons to withdraw a participant from the study.

1. Participant request to be withdrawn from the study.
2. Safety concerns (adverse events or reactions etc.).
3. Investigator discretion (will usually be related to patient safety).
4. Treatment failure (the need for a longer parenteral therapy or hospital admission).

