9.3 Follow Up After Last Treatment

Subjects will be assessed in the office within 24 hours of termination of at home treatment.

Assessments will include:

- Weight, Blood pressure, Heart Rate, Respiratory Rate, Temperature
- Physical examination
- NYHA classification
- Injection site assessment
- Blood test (Sodium, chloride, potassium, bicarbonate, Bun, Creatine, magnesium, pro BNP)
- Dyspnea scale (appendix B)
- Assessment for adverse events
- Assessment for interval hospitalizations, ED visits, or unscheduled clinic visits

At this visit, the physician can decide if the treatment should be extended for four extra days (after the initial three days of therapy). If there is no interval improvement, the physician can withdraw the subjects from the trial for safety reasons. The initial follow up assessment will be included in the final analysis. Patients who show improvement with initial treatment (3 days or 3 day plus up to 4 days at home) may be offered 3 extra days of “rescue treatment” as needed within 30 days of enrollment in the trial. During the “rescue treatment” they will be evaluated daily by the visiting nurse and at follow up if they need further assessment as done during the treatment phase.

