13.6 Relatedness of AE or SAE to IP

Using his/her best medical judgment and the available information on the Investigational Product (IP), the Investigator will determine if the AE and or SAE caused the observed symptoms associated with the event.

- **Not related:** Unestablished reasonable causal relationship between the IP and the AE.
- **Unlikely related:** No temporal association or cause of the event has been identified.
- **Possibly related:** There is reasonable evidence to suggest a causal relationship between the drug and adverse event, however there could be other confounders to the AE
- **Related:** There is a causal relationship

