19 APPENDICES

Appendix A. Schedule of Assessments

	Screening	Baseline	Treatment*	First Post Treatment	Second Post Treatment (if applicable)	Post-Treatment Visit
Day	0	0	Daily (3 ± 4 days)	Within 24hrs of last treatment	Within 24hrs of last treatment	30±3days after first dose
Informed Consent	X					
Pregnancy Test*	X					
Training		X				
Medical History		X				
Initial sc2Wear Treatment		X				
Weight		X	X	X	X	X
Height		X				
HF Physical Exam		X	X	X	X	X
NYHA		X		X	X	X
Baseline Labs ^a		X				
Monitoring labs ^b			X	X	X	X
Vitals Signs ^c		X	X	X	X	X
Dyspnea Scale		X	X	X	X	X
Electrolyte correction		X	X			
Injection Site Inspection			X	X	X	X
Current Medication	X	X	X	X	X	X
Adverse Events ^d		X	X	X	X	X

- * To be performed by Steward Home Care and Hospice in accordance with standard practices for homebound heart failure patients
- a. Baseline laboratory panel (Sodium, potassium, Bun, Cr, Mg, pro-BNP, Hemoglobin and Hematocrit)
- b. Monitoring laboratory panel: (sodium, chloride, bicarbonate, potassium, Bun, Cr, Mg)
- c. Vital signs: Blood pressure, heart rate, temperature, respiratory rate
- d. Adverse Events: Major Event: death, hospitalization, MACE (major adverse cardiac event); Minor: ER visit for acute decompensated heart failure (excluding study related visits), admission to SNF or similar inpatient facility

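### Section 13.2 counts a hospital admission as serious only if the therapy caused it, and lets admissions after failed home diuresis be left out of the SAEs

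*Combined protocol and SAP*

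**What the plan says.** Section 13.2 gives the criteria that make an event serious. The one on hospitalization reads "Inpatient hospitalization due to the therapy. This may not include patients who choose to withdraw from the study and opt to be admitted", and the same sentence adds "patients who are withdrawn from the study for better diuresis in the hospital". It does not say who decides whether an admission is left out, or on what criterion.

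Three other places describe what happens when home treatment does not work:

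- Section 6.3 lists as a reason for withdrawal "Treatment failure (the need for a longer parenteral therapy or hospital admission").
- Section 9.3 says of the post-treatment visit: "If there is no interval improvement, the physician can withdraw the subjects from the trial for safety reasons".
- The synopsis (Section 2, Study Procedures) says of patients who still need parenteral diuresis after 7 days that "they will be converted to usual care at that time, which may require inpatient care".

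Causality has its own section, 13.6, headed "Relatedness of AE or SAE to IP", with a four-level scale. Footnote d of Appendix A classes adverse events separately and begins "Major Event: death, hospitalization, MACE (major adverse cardiac event"), with no causal condition. The synopsis (Statistical Analysis) places under the primary outcome a "Description of the seriousness, severity, relatedness of all adverse events observed during the study period".

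**The concern.** Seriousness and causality are separate attributes of an event, and the plan intends to describe both. If an admission must be caused by the therapy before it is serious, relatedness has been decided before the relatedness scale is applied. Admissions judged unrelated then drop out of the SAE set instead of appearing in it as unrelated.

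The exception adds to this because it is aimed at admissions for inadequate diuresis. In a study of home treatment as an alternative to inpatient care, that is one of the most foreseeable bad outcomes.

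Safety and tolerability form one of the two objectives in Section 4. Section 13.9 names only SAEs as events to be made available to the IRB. Section 5 has the sponsor and the manufacturer review the pilot results before 40 more patients are recruited. All of these depend on the SAE classification.

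**Working it through.** **The plan's own figure.** Section 14 states 59 evaluable subjects, 95% confidence and 5% incidence.

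- Probability of at least one event: 1 − (1 − 0.05)^59 = 0.9515.
- Smallest n: ln 0.05 / ln 0.95 = 58.40, rounded up to 59.
- One-sided 95% upper limit for 0 of 59: 1 − 0.05^(1/59) = 4.95%.

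The figure reproduces. It assumes that every event of the type is counted. Zero hospitalization SAEs under Section 13.2 would therefore not show that the incidence of admission is below 5%.

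**The seriousness criteria compared.** Death, life-threatening event, disability or incapacity, and congenital anomaly carry no causal condition in Section 13.2. Hospitalization alone does. The opening of Section 13 says that an AE does not by itself imply causality. The Section 13.6 scale applies to SAEs and has a not-related level. For an SAE that qualifies only through hospitalization, that level would be empty by construction.

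**How an admission reaches the exception.**

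1. Section 6.3 gives the direct route: need for admission is treatment failure, treatment failure is a reason for withdrawal, and Section 13.2 exempts patients withdrawn for inpatient diuresis.
2. Section 9.3 allows withdrawal for lack of improvement. It does not mention admission, so this route is possible but not stated.
3. The synopsis allows conversion to usual care, possibly inpatient. It does not call this withdrawal, so this route is also possible but not stated.

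**What is still captured.** Withdrawn patients are monitored for 30 days (6.3). Interval hospitalizations are assessed at the post-treatment and Day 30 visits (9.3, 9.4). Worsening-HF admissions count in a 30-day endpoint (10.1). AEs are documented with a narrative (13.9). Section 13.9 also asks for AEs and SAEs up to 30 days after completion to be reported, but names no recipient.

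**What is not captured as serious.** The causal condition covers every admission. Section 13.3 anticipates stroke, arrhythmia, syncope and acute kidney injury. An admission for one of these, judged not due to the therapy, is outside the HF-hospitalization endpoint. It is also not an SAE unless another criterion in 13.2 applies.

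**Size.** Section 14 plans an analysis of the first 20 patients and a combined analysis of 60. For each patient whose only serious event is an omitted admission, the percentage of patients with an SAE falls by:

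- combined: 1/60 = 1.67 percentage points;
- pilot: 1/20 = 5.0 percentage points.

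The documents give neither an admission rate for this population nor the share that would be left out. As an assumption only, 30-day admission rates of 5% to 25% would mean 0.05 × 60 = 3 to 0.25 × 60 = 15 patients admitted. The share omitted could be anything from none to all of them. That range is too wide to serve as an estimate of the total.

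**The case against.** The strongest reply is that little is lost. The admissions remain observed, the study is descriptive with no comparison group, and Appendix A still lists hospitalization as a major event. Section 16 makes study data available to the IRB for inspection. Keeping lack of efficacy out of the SAEs could be deliberate, since HF admission is an efficacy endpoint (10.1) and worsening HF is an anticipated event (13.3). The 1.7 and 5.0 points are also plain 1/n arithmetic on a percentage that the plan does not name as an endpoint.

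Some of this stands. The harm is confined to classification, only Section 6.3 links failure, withdrawal and admission directly, and the per-patient figures do not show how often the problem would arise. The Appendix A grouping is never equated with the SAE definition, so the difference between the two supports the point without proving it.

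The rest does not answer it. Inspection access is not SAE reporting. Section 13.2 states no policy of treating HF admissions as efficacy outcomes, and such a policy could not explain a causal condition that also covers non-HF admissions.

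A last worry is that counting all admissions would bring in planned ones. It would not, because an SAE must still be an unfavourable or unintended occurrence under Section 13.

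**Conclusion.** The concern holds. As written, Section 13.2 mixes causality with seriousness and permits admissions after failed home diuresis to be left out of the SAEs, with no stated criterion for doing so. Whether the wording of the exception is read as permission or as exclusion, such admissions can be omitted. Fatal, life-threatening or disabling cases remain SAEs.

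The SAE count, the description of seriousness and the SAEs made available to the IRB can be understated; data capture is not affected. The per-patient effects assume full analysis sets of 60 and 20 and a patient with no other serious event. The total is unknown and may be zero. Confidence in the reading of the text is high. This should be fixed, but it does not invalidate the study.

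**What to change.** In Section 13.2, make the criterion any inpatient hospitalization regardless of cause, and delete the sentence that exempts patients who withdraw or are withdrawn. Flag admissions for worsening HF and tabulate them as a separate subset of the SAEs that the IRB also sees. They then stay recognisable as anticipated events (13.3) and as efficacy outcomes (10.1). Leave causality to the Section 13.6 rating. Footnote d of Appendix A needs no change.

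The cost is a wording change and one more subset in the SAE table. Section 13.9 already asks for a narrative on every AE and SAE, so that requirement does not grow. Whether the adverse-event form can already carry the flag cannot be checked, because Appendix F is given by title only. The downside is a higher SAE count that includes admissions unrelated to the product; the relatedness rating and the flag keep these distinguishable. No sample size or treatment rule is affected.

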13.7 Severity of AEs

The severity of AEs should be documented using the following criteria.

- Mild: symptom does not influence performance. Subject barely notices it
- Moderate: Subject's daily performance is affected. Treatment may be needed.
- Severe: Subject experiences severe discomfort. Treatment necessary

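### Section 13.2 sets two thresholds for incapacity, the looser of which overrides the stricter, and separately has no seriousness criterion for urgent treatment without admission

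*Combined protocol and SAP*

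**What the plan says.** Section 13.2 opens with "Serious Adverse Event (SAE) refers to any event that result in the following" and gives six bullets. Four bear on this point:

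- The second bullet is "Life-threatening AE".
- The third is "A disability or incapacity", with no limit on degree or duration.
- The fourth is "Inpatient hospitalization due to the therapy". A rider says this may leave out patients who withdraw and choose admission, and "patients who are withdrawn from the study for better diuresis in the hospital".
- The fifth is "Persistent or significant incapacity or substantial disruption of the ability to conduct normal life functions".

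Death and congenital anomaly complete the list. No bullet concerns treatment given to avert one of these outcomes.

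Other sections touch on the same events. Section 13.7 uses need for treatment to grade severity, not seriousness; its Moderate grade includes "daily performance is affected. Treatment may be needed". Footnote d of Appendix A sorts adverse events into Major and Minor. Any hospitalization is Major, and the Minor class begins "Minor: ER visit for acute decompensated heart failure (excluding study related visits". Section 13.3 anticipates arrhythmias, transient ischemic attacks, presyncope and syncope.

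The label is used in two places. The synopsis, under Statistical Analysis, puts a description of the seriousness of all adverse events under the primary outcome. Section 13.9 has the investigator make SAEs available to the IRB.

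**The concern.** A list of this kind should lead two assessors with the same event to the same label. Here the third and fifth bullets draw the line for incapacity in different places, and nothing says which was intended. A qualifier that has no effect looks like a drafting slip, and an assessor may reasonably take the more specific bullet as the rule. The plan expects events that could fall between the two: Section 11 names weakness, lethargy, drowsiness and hypotension, and Section 13.3 names presyncope and syncope.

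The second matter is independent of the first. Patients are treated at home as an alternative to inpatient care, so important events may well be handled in the emergency room or at home without admission. The list has no entry for them unless they are life-threatening or incapacitating.

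At stake are the seriousness tabulation and the set of events the IRB sees. The study has 60 patients and descriptive analysis only, so a few events labelled differently would show in the reported SAE count. Up to three hospitals may apply the list in the Evaluation Phase.

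**Working it through.** **1. The plan's own safety figure.** Section 14 says 59 evaluable subjects suffice to detect, with 95% confidence, events of 5% incidence or more. Check: 1 − 0.95^59 = 0.9515, and ln 0.05 / ln 0.95 = 58.40, which rounds up to 59. The figure reproduces. It is not tied to the SAE label, so this point does not change it.

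**2. How the two incapacity bullets combine.** Let A be any disability or incapacity (third bullet), B persistent or significant incapacity, and C substantial disruption of normal functioning (B and C form the fifth bullet). An event is serious if it falls in A or B or C. B lies inside A, so this reduces to A or C. The qualifier in B therefore excludes nothing, and the fifth bullet can only add events, through C. The duplication cannot lower the count if the list is applied as written. It can admit brief incapacity, or produce inconsistent labels if someone applies the fifth bullet alone.

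**3. Test cases against the list.** The cases are illustrative; the documents give no rates for them.

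| Event | Third bullet | Fifth bullet | Other bullets | Result |
|---|---|---|---|---|
| Unable to stand for an hour from dizziness, full recovery | Met, read literally | Arguably not met | Not met | SAE as written; non-serious to an assessor using the fifth bullet only |
| Lasting or marked incapacity | Met | Met | Not needed | SAE either way |
| Substantial disruption without incapacity | Not met | Met | Not needed | SAE through the fifth bullet only |
| Arrhythmia treated in the emergency room, discharged, not life-threatening, no incapacity | Not met | Not met | Not met | Non-serious AE |
| Admission judged not due to the therapy, no other bullet met | Not met | Not met | Fourth not met | Non-serious under 13.2; Major under footnote d |

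The first row shows the over-inclusion, the fourth the missing criterion, and the fifth a conflict between Section 13.2 and Appendix A.

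**4. What depends on the label.** The safety endpoints in Sections 10.2 and 14 are the incidence of adverse events and discontinuation for skin reaction. Neither uses seriousness. The seriousness description in the synopsis and the SAE set in Section 13.9 do.

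**5. Illustration under an assumption.** Suppose a reader takes the Section 14 statement to refer to recorded SAEs, which it does not say, and a share s of truly serious events meets no bullet. The chance of recording at least one SAE of 5% true incidence in 59 patients is 1 − (1 − 0.05(1 − s))^59. The limit on true incidence implied by none recorded is (1 − 0.05^(1/59))/(1 − s) = 4.95%/(1 − s).

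| Assumed s | Chance of recording at least one | Implied limit |
|---|---|---|
| 0 | 95.2% | 4.95% |
| 10% | 93.4% | 5.5% |
| 25% | 89.5% | 6.6% |
| 50% | 77.5% | 9.9% |

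No value of s can be taken from the documents.

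**The case against.** The strongest reply has four parts.

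- **Assessors do not choose a bullet.** Any bullet suffices, so the duplicate is redundant wording. This stands as far as it goes: a reader might infer that the duplication can push the count either up or down, and step 2 shows it cannot push it down. It does not answer the over-inclusion of brief incapacity, or the risk that a specific bullet is read as displacing a general one.
- **Nothing in the documents requires an urgent-treatment criterion.** This stands. Section 17.1 commits to ICH GCP and 21 CFR part 312 without reproducing their text, so a breach of a required definition cannot be argued from the documents. The added bullet is a design recommendation.
- **Events treated in the emergency room are not lost.** This stands for the data. Sections 9.3 and 9.4 ask about ED and unscheduled visits, footnote d covers emergency visits for decompensation, and Section 13.9 requires all AEs to be documented and notified to the principal investigator within 24 hours. What such an event lacks is the serious label and the route to the IRB that goes with it.
- **Severity and the Major/Minor scale are separate from seriousness.** This also stands. A reader might infer that a Moderate event becomes an SAE through the third bullet, but affected daily performance is not incapacity and the documents never equate them. A reader might likewise infer that the Minor class makes an emergency visit non-serious, but nothing links footnote d to Section 13.2. The absence of any stated link is itself worth one clarifying sentence.

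**Conclusion.** The point holds in two separate parts. The unqualified incapacity bullet voids the qualifier in the later one, so brief incapacity can be counted as an SAE and assessors can differ. Independently, the list has no criterion for urgent treatment without admission, so such an event is tabulated as non-serious unless judged life-threatening or incapacitating. Any under-count comes from that absence, not from the duplicate. In the same list, the limit of hospitalization to that caused by the therapy conflicts with footnote d, which counts any hospitalization as Major.

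The size cannot be estimated. A reader might put counts on it, for example 60 × 0.10 = 6 extra or 60 × 0.05 = 3 omitted, but those rates would be guesses, and the first also assumes that every brief limitation of activity is classed as incapacity. The conclusion rests on reading the list as satisfied by any single bullet, which is how its opening sentence runs. It affects the descriptive seriousness output and IRB reporting; sample size and the incidence of all AEs are untouched. This is a minor improvement and cheap to make.

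**What to change.** Amend Section 13.2 and Appendix A in one edit:

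1. Delete the third bullet and insert disability beside incapacity in the fifth, so that both carry the same qualifier. Deleting the third bullet alone would remove the list's only mention of disability.
2. Add one bullet for an event that, in the investigator's judgement, needed urgent treatment, for example in the emergency room, to prevent one of the other listed outcomes.
3. State in footnote d that the Major/Minor scale does not decide seriousness.
4. Reconcile the hospitalization bullet and its rider with footnote d, so that the same admission is not left out of one and counted in the other without explanation.

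This changes protocol wording, with IRB review of the amendment as Section 17.4 requires. It adds no visit or assessment and does not alter the analysis. The downside is that a few more events would be reported as SAEs.
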